8.4 Safety reporting and medical management

8.4.1 Reporting of serious adverse events

All SAEs have to be reported, whether or not considered causally related to the IP, or to the study procedure(s). All SAEs will be recorded in the eCRF.

If any SAE occurs in the course of the study, then investigators or other site personnel inform the appropriate AstraZeneca representatives within 1 day ie, immediately but **no later than 24 hours** of when he or she becomes aware of it.

The designated AstraZeneca representative works with the investigator to ensure that all the necessary information is provided to the AstraZeneca Patient Safety data entry site **within**

1 calendar day of initial receipt for fatal and life-threatening events **and within 5 calendar days** of initial receipt for all other SAEs.

For fatal or life-threatening AEs where important or relevant information is missing, active follow-up is undertaken immediately. Investigators or other site personnel inform AstraZeneca representatives of any follow-up information on a previously reported SAE within 1 calendar day ie, immediately but **no later than 24 hours** of when he or she becomes aware of it.

Once the investigators or other site personnel indicate an AE is serious in the EDC system, an automated email alert is sent to the designated AstraZeneca representative.

If the EDC system is not available, then the investigator or other study site staff reports a SAE to the appropriate AstraZeneca representative by telephone.

The AstraZeneca representative will advise the investigator/study site staff how to proceed.

Section 5.4 of the osimertinib and savolitinib investigator brochures provides information related to the emerging safety profile of both study treatments. For further guidance on the definition of a SAE, see [Appendix B](#) of the Clinical Study Protocol.

8.4.2 Pregnancy

All pregnancies and outcomes of pregnancy during the course of study and within 6 weeks of the last dose of osimertinib should be reported to AstraZeneca except for:

- If the pregnancy is discovered before the study patient has received any study drug.

If a pregnancy is reported, the investigator should inform the sponsor within 24 hours of learning of the pregnancy.

Abnormal pregnancy outcomes (eg, spontaneous abortion, foetal death, stillbirth, congenital anomalies, ectopic pregnancy) are considered SAEs.

8.4.2.1 Maternal exposure

If a patient becomes pregnant during the course of the study, IP should be discontinued immediately.

Pregnancy itself is not regarded as an AE unless there is a suspicion that the IP under study may have interfered with the effectiveness of a contraceptive medication. Congenital abnormalities/birth defects and spontaneous miscarriages should be reported and handled as SAEs. Elective abortions without complications should not be handled as AEs. The outcome of all pregnancies (spontaneous miscarriage, elective termination, ectopic pregnancy, normal birth or congenital abnormality) should be followed up and documented even if the patient was discontinued from the study.

If any pregnancy occurs in the course of the study, then the investigator or other site personnel informs the appropriate AstraZeneca representatives within 1 day ie, immediately but **no later than 24 hours** of when he or she becomes aware of it.

The designated AstraZeneca representative works with the investigator to ensure that all relevant information is provided to the AstraZeneca Patient Safety data entry site within 1 or 5 calendar days for SAEs (see Section [8.3.2](#)) and within 30 days for all other pregnancies.

The same timelines apply when outcome information is available.

The PREGREP module in the eCRF is used to report the pregnancy.

8.4.2.2 Paternal exposure

Male patients should refrain from fathering a child or donating sperm during the study and 6 months following the last dose.

Pregnancy of the patient's partner is not considered to be an AE. However, the outcome of all pregnancies (spontaneous miscarriage, elective termination, ectopic pregnancy, normal birth or congenital abnormality), occurring from the date of the first dose until 6 months after the last dose and as indicated by previous studies (pre-clinical and clinical) should, if possible, be followed up and documented in the Pregnancy Report Form. Consent from the partner must be obtained before the Pregnancy Report Form is completed.

8.4.3 Reporting of overdose

A maximum tolerated dose has not been established for osimertinib or savolitinib, therefore an overdose is any dose which exceeds the daily dose that is defined in this clinical study protocol.

- An overdose with associated AEs is recorded as the AE diagnosis/symptoms on the relevant AE modules in the eCRF and on the Overdose eCRF module.
- An overdose without associated symptoms is only reported on the Overdose eCRF module.

If an overdose on an IMP or AstraZeneca NIMP occurs in the course of the study, the investigator or other site personnel inform appropriate AstraZeneca representatives immediately, but **no later than 24 hours** of when he or she becomes aware of it.

The designated AstraZeneca representative works with the investigator to ensure that all relevant information is provided to the AstraZeneca Patient Safety data entry site within 1 (Initial Fatal/Life-Threatening or follow-up Fatal/Life-Threatening) or 5 (other serious initial and follow-up) calendar days for overdoses associated with an SAE (see Sections [8.3.2](#) and [8.4.1](#)) and within 30 days for all other overdoses.

8.4.4 Medication Error, Drug Abuse, and Drug Misuse

8.4.4.1 Timelines

If an event of medication error, drug abuse, or drug misuse occurs during the study, then the investigator or other site personnel informs the appropriate AstraZeneca representatives within 1 calendar day, ie, immediately but no later than 24 hours of when they become aware of it.

The designated AstraZeneca representative works with the investigator to ensure that all relevant information is completed within 1 (Initial Fatal/Life-Threatening or follow-up Fatal/Life-Threatening) or 5 (other serious initial and follow-up) calendar days if there is an SAE associated with the medication error, drug abuse, or drug misuse (see Sections [8.3.2](#) and [8.4.1](#)) and within 30 days for all other events.

8.4.4.2 Medication Error

For the purposes of this clinical study a medication error is an unintended failure or mistake in the treatment process for an IMP or AstraZeneca NIMP that either causes harm to the patient or has the potential to cause harm to the patient.

The full definition and examples of medication error can be found in [Appendix B 8](#).

8.4.4.3 Drug Abuse

Drug abuse is the persistent or sporadic intentional, non-therapeutic excessive use of IMP or AstraZeneca NIMP for a perceived reward or desired non-therapeutic effect.

The full definition and examples of drug abuse can be found in [Appendix B 8](#).

8.4.4.4 Drug Misuse

Drug misuse is the intentional and inappropriate use (by a study patient) of IMP or AstraZeneca NIMP for medicinal purposes outside of the authorised product information, or for unauthorised IMPs or AstraZeneca NIMPs, outside the intended use as specified in the protocol and includes deliberate administration of the product by the wrong route.

The full definition and examples of drug misuse can be found in [Appendix B 8](#).

8.4.5 Management of IP-related toxicities

8.4.5.1 Management of osimertinib-related toxicities

Potential osimertinib-related toxicities during the course of the study can be managed by interruption of the dose of osimertinib or dose reductions (see [Appendix I Section I 1](#)). Repeat dose interruptions are allowed as required. If a patient experiences a CTCAE Grade 3 (CTCAE version 5.0) and/or unacceptable toxicity, dosing will be interrupted and supportive therapy administered as required in accordance with local practice/guidelines. If the toxicity resolves or reverts to \leq CTCAE Grade 2 after 3 weeks of onset, treatment with osimertinib

may be restarted at the same dose (80 mg) or a lower dose (40 mg) using the rules in [Appendix I Section I 1](#) and with discussion and agreement with the AstraZeneca Study Team Physician as needed. There will be no individual modifications to dosing schedule in response to toxicity, only potential dose reduction or dose modification. If the toxicity does not resolve to \leq CTCAE Grade 2 after 3 weeks, then the patient should be withdrawn from the study and observed until resolution of the toxicity. Osimertinib can be dose reduced to 40 mg od: if the reduced dose of 40 mg od is not tolerable, no further dose reduction is allowed and study treatment should be discontinued. Once a dose is reduced escalation is not permitted.

Dose modifications are permitted in the management of IP-related toxicities as described in [Table 11](#) with further information being provided in [Appendix I Section I 1](#).

Dose modification guidelines for QTc prolongation are shown in [Table 12](#).

Table 11 Osimertinib dose adjustment information for adverse reactions

Target organ	Adverse reaction ^a	Dose modification
Pulmonary	ILD/pneumonitis	Permanently discontinue osimertinib
Other	Grade 3 or higher adverse reaction	Withhold osimertinib for up to 3 weeks
	If Grade 3 or higher adverse reaction improves to Grade 0 to 2 after withholding of osimertinib for up to 3 weeks	Osimertinib may be restarted at the same dose (80 mg) or a lower dose (40 mg)
	Grade 3 or higher adverse reaction that does not improve to Grade 0 to 2 after withholding for up to 3 weeks	Permanently discontinue osimertinib

^a The intensity of the clinical adverse events graded by the National Cancer Institute CTCAE Version 5.0.

ILD Interstitial lung disease.

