8.4.5.2 Management of savolitinib-related toxicities

Potential savolitinib-related toxicities during the course of the study can be managed as medically indicated and with interruption of the dose of savolitinib or dose reductions as appropriate, **unless symptoms are associated with hypersensitivity** (see [Appendix I Section I 3](#)). Repeat dose interruptions are allowed as required, taking into consideration the additional precautions for restart of savolitinib as illustrated in [Appendix I](#). For each patient the savolitinib dose can be reduced a maximum of 2 times ([Table 9](#)). No dose re-escalations are allowed.

Dose modification guidelines for QTc prolongation are shown in [Table 12](#).

Table 12 Dose modifications for QTc prolongation

NCI CTCAE Toxicity Grade	Action with savolitinib	Action with osimertinib
Grade 0, 1, or 2	None	None
Grade 3 Patients with QTcF prolongation to >500 msec on at least 2 separate ECGs If the toxicity does not resolve to QTcF <481 msec within 21 days	Hold dosing and follow algorithm below: Consult with cardiologist to validate ECG finding. Ensure cardiac surveillance and take actions in accordance with clinical standards. Regular ECGs performed until resolution to QTcF <481 msec and then restart drug at one reduced dose level.* Permanently discontinue study drug and consult with a cardiologist for further management as clinically indicated.	Hold dosing and follow algorithm below: Withhold until QTc interval is <481 msec or recovery to baseline if baseline QTc is more than 481 msec within 21 days of onset, then restart at a reduced dose (40 mg) or at 80 mg (at the discretion of the investigator). Permanently discontinue osimertinib.
Grade 4 QTcF \geq 501 or >60 msecs change from baseline and Torsade de pointes or polymorphic ventricular tachycardia or signs/symptoms of serious arrhythmia	Permanently discontinue study drug and consult with a cardiologist for further management as clinically indicated.	Permanently discontinue osimertinib.

CTCAE Common Terminology Criteria for Adverse Events; ECG Electrocardiogram; NCI National Cancer Institute; QTc corrected QT interval; QTcF corrected QT interval using Fridericia's formulas.

***For French sites only**, as per ANSM advice, the patient must remain hospitalised with continuous cardiac monitoring (ECG) until specialist advice is obtained by a cardiologist.

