Appendix I Dose modifications for the management of adverse events

I 1 Osimertinib dose modification and guidance

Osimertinib management should be in accordance with the local label in the first instance.

If a patient experiences a CTCAE Grade 3 and/or unacceptable toxicity dosing will be interrupted and supportive therapy administered as required in accordance with local practice/guidelines.

If a toxicity resolves or reverts to \leq CTCAE Grade 2 within 3 weeks of onset, treatment with osimertinib may be restarted at the same dose (80 mg) or a lower dose (40 mg) using the rules below for dose modifications ([Table 19](#)) and with discussion and agreement with the AstraZeneca Study Team Physician as needed. There will be no individual modifications to dose regimen in response to toxicity, only potential dose reduction or dose interruption.

If the toxicity does not resolve to \leq CTCAE Grade 2 after 3 weeks, then the patient should be withdrawn from the study and observed until resolution of the toxicity ([Table 20](#)).

Table 19 Dose reduction for osimertinib to manage adverse events

	Starting osimertinib dose 80 mg
Reduced dose -1	40 mg

On resolution of toxicity within 3 weeks:

If an AE subsequently requires dose interruption, osimertinib may restart at the same dose or the reduced dose, on resolution/improvement of the AE at the discretion of the investigator.

Table 20 Osimertinib Dose Adjustment Information for Adverse Reactions

Target organ	Adverse reaction ^a	Dose modification
Pulmonary	ILD/pneumonitis	Permanently discontinue osimertinib
Cardiac	QTc interval > 500 msec on at least 2 separate ECGs	Withhold osimertinib until QTc interval is < 481 msec or recovery to baseline if baseline QTc is ≥ 481 msec within 3 weeks of interruption, then restart at a reduced dose (40 mg) or at 80 mg (at the discretion of the investigator), to allow for situations where causality in relation to osimertinib may be difficult to determine.
	QTc interval prolongation with signs/symptoms of serious arrhythmia, symptomatic congestive heart failure	Permanently discontinue osimertinib
Other	Grade ≥ 3 adverse reaction	Withhold osimertinib for up to 3 weeks
	If Grade ≥ 3 adverse reaction improves to Grade 0 – 2 after withholding osimertinib for up to 3 weeks	Osimertinib may be restarted at the same dose (80 mg) or at a lower dose (40 mg)

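### The 3-week limit that decides whether osimertinib may be restarted has no uniform start point, and the consequence of missing it differs between text and tables

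*Protocol*

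**What the plan says.** **Grade 3 toxicity, running text.** Protocol Section 8.4.5.1 interrupts dosing and then permits restart if the event falls to "CTCAE Grade 2 after 3 weeks of onset, treatment with osimertinib" may be resumed at 80 mg or 40 mg, under the rules of Appendix I 1. The text of Appendix I 1 permits restart on reversion to "CTCAE Grade 2 within 3 weeks of onset". Both then say that if the event has not come down to "CTCAE Grade 2 after 3 weeks, then the patient should be withdrawn from the study and observed until resolution of the toxicity".

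**Grade 3 toxicity, tables.** Table 11, in the same Section 8.4.5.1, permits restart as follows: "If Grade 3 or higher adverse reaction improves to Grade 0 to 2 after withholding of osimertinib for up to 3 weeks". It permanently discontinues osimertinib for a "Grade 3 or higher adverse reaction that does not improve to Grade 0 to 2 after withholding for up to 3 weeks". Table 20 in Appendix I 1 follows Table 11.

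**QTc prolongation.** Table 12 (Section 8.4.5.2) asks for recovery "within 21 days of onset, then restart at a reduced dose (40 mg) or at 80 mg". Table 20 asks for recovery "within 3 weeks of interruption, then restart at a reduced dose (40 mg) or at 80 mg". Table 25 (Appendix I 3.5) counts 21 days from onset, and Table 21 (Appendix I 1.2) gives 21 days without saying from when.

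**Stopping versus withdrawal.** Section 7.1 states that stopping study treatment is not the same as complete withdrawal from the study. Sections 7.1.2 and 7.1.3 keep patients who stop treatment in follow-up.

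**The concern.** The 3-week limit is the line between restarting one of the two study drugs and stopping it for good. A site has to know when the count begins. Onset and hold are different dates whenever a toxicity begins before the site acts on it, which is possible because from Cycle 2 most clinic assessments fall on Day 1 of a 28-day cycle.

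If sites count from different dates, patients with the same course of events can be managed differently, and AE-related discontinuations are not counted on one basis. The discontinuation rate due to AEs is a named safety endpoint (Protocol Section 3), and SAP Section 4.2.3.2 tabulates TEAEs leading to discontinuation of each study treatment.

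The difference in consequence is a separate fault. Read literally, withdrawal from the study ends more than osimertinib dosing, whereas Section 7.1.3 requires tumour assessments to continue in patients who stop treatment before progression.

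**Working it through.** The documents give no figure to reproduce, so the check sets the passages side by side and then counts days.

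**Step 1. Where each clock starts**

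| Place in Protocol | Event | Limit | Counted from |
|---|---|---|---|
| Section 8.4.5.1 text | Grade 3 | 3 weeks, worded *after* | onset |
| Appendix I 1 text | Grade 3 | 3 weeks, worded *within* | onset |
| Table 11 | Grade 3 or higher | up to 3 weeks | withholding |
| Table 20, general rows | Grade 3 or higher | up to 3 weeks | withholding |
| Table 12 | QTc | 21 days | onset |
| Table 25 | QTc | 21 days | onset |
| Table 20, QTc row | QTc | 3 weeks | interruption |
| Table 21 | QTc | 21 days | not stated |

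The running text triggers on Grade 3 and/or unacceptable toxicity and the tables on Grade 3 or higher, so the comparison is made at Grade 3, where both apply. Appendix I 1 disagrees with itself: its text uses onset and its Table 20 uses withholding or interruption.

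**Step 2. *After* against *within***

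Taken literally, a patient who recovers 25 days after onset may restart under Section 8.4.5.1 but not under Appendix I 1. A patient who recovers 10 days after onset may restart under Appendix I 1 but is not covered by the Section 8.4.5.1 restart sentence.

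**Step 3. Onset clock against withholding clock**

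Let R be the days from onset to recovery (Grade 2 or lower, or the QTc threshold) and L the days from onset to hold. Three weeks is 3 × 7 = 21 days.

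- Onset clock: restart allowed if R ≤ 21.
- Withholding clock: restart allowed if R − L ≤ 21, that is R ≤ 21 + L.
- The clocks disagree when 21 < R ≤ 21 + L, a window of L days. Inside it the withholding clock allows restart and the onset clock does not.

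The documents give no value for L. The values below are assumptions.

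| Assumed L | Upper end, 21 + L | R affected |
|---|---|---|
| 0 days | 21 | none |
| 4 days | 25 | 22 to 25 days |
| 7 days | 28 | 22 to 28 days |

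Example with L = 4: onset on Day 1, hold on Day 5, Grade 2 on Day 24. From onset, 24 − 1 = 23 days, which exceeds 21. From the hold, 24 − 5 = 19 days, which does not. Appendix I 1 text does not allow restart; Tables 11 and 20 do.

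**Step 4. Consequence of missing the limit**

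The text of Section 8.4.5.1 and of Appendix I 1 withdraws the patient from the study. Tables 11 and 20 permanently discontinue osimertinib and say nothing about withdrawal. The withdrawal sentence in Appendix I 1 cites Table 20, so the cited table does not carry the consequence stated in the text. Section 7.1 makes the two outcomes different.

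**The case against.** The strongest reply is that the conflict is smaller than it looks.

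- **The *after* wording.** Section 8.4.5.1 sends restart to the Appendix I 1 rules, which say *within*. Its own stop sentence treats 3 weeks as an outer limit, and a literal *after* would contradict both that sentence and Table 11 just below it. It could also be meant as status at the 3-week mark. This stands: *after* is most likely a slip.
- **The narrow window.** Both texts interrupt dosing at Grade 3. If the hold is made on the day of onset, the two clocks coincide. For QTc, the event is found on ECGs, so the delay may well be short. This stands as a limit on size.
- **Room for judgement.** Restart is permissive, the sponsor's study physician is consulted as needed, and Appendix I 1 puts the local label first. This stands in part. The other branch, withdrawal or permanent discontinuation, is directive, and nothing in the protocol says whether the onset or the withholding clock prevails.

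A reader might infer that the same patient routinely receives opposite instructions. The documents do not support that: outside the window in Step 3 the onset and withholding clocks agree, and the literal *after* reading is implausible in context.

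The reply does not remove the mixed start points, which occur even within Appendix I 1, or the conflicting consequence.

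**Conclusion.** The plan needs correcting on this point. The limit between restart and permanent discontinuation of osimertinib is counted from onset in some places, from withholding or interruption in others, and from nothing stated in Table 21. Answers differ only for patients with 21 < R ≤ 21 + L. The number of such patients cannot be derived, because the documents give neither the delay L nor the distribution of recovery times; the windows shown rest on assumed delays of 0, 4 and 7 days. The conflict over consequence does not depend on L and applies to any patient who misses the limit.

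A reader might go further and infer bias in the randomised efficacy comparison. The documents do not show this. The Contribution of Components Analysis Set follows randomisation regardless of treatment received, PFS counts events regardless of withdrawal from therapy, and osimertinib and its placebo are blinded and share one dose-reduction table (Protocol Table 8). The discontinuation rate due to AEs is summarised descriptively. What is at stake is consistent patient management and consistent counting of AE discontinuations. Which rule is clinically right is not judged here.

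**What to change.** Reconcile Section 8.4.5.1, the Appendix I 1 text and Tables 11, 12, 20, 21 and 25 so that they share:

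1. one stated start point for the 3-week (21-day) count;
2. one wording, replacing *after* in the Section 8.4.5.1 restart sentence or explaining it;
3. one consequence when the limit is missed, either withdrawal from the study or stopping osimertinib, expressed in the terms of Section 7.1.

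The sponsor's medical team has to make the clinical choice. Tables 21 and 25 must be included, or the QTc rules stay inconsistent after the change. The cost is a protocol clarification and notice to sites; no change to sample size, endpoints or planned analyses follows from it.
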